
INNOVATION

The challenge for this study is to further develop and implement nerTMS as a tool for stimulating language recovery in patients with chronic post-stroke aphasia. This challenge will be addressed by conducting a randomized, sham-controlled, dose-response trial of nerTMS in order to provide class I data from a phase III treatment trial investigating fMRI-targeted treatment for chronic post-stroke aphasia (**AIM 1**). While there is evidence that nerTMS applied to the affected hemisphere may improve post-stroke motor recovery [58] and when applied to the language-dominant hemisphere in controls may promote better language skills, nerTMS has not been tested in treatment of post-stroke aphasia or in combination with other restorative therapies (CIAT; **AIM 3**). The potential impact of this study is tremendous with the potential to improve the quality of life in hundreds of thousands of Americans. We will demonstrate that nerTMS applied to the peri-stroke regions defined by fMRI promotes language recovery, and we will determine the most efficacious and the safest dose of nerTMS (**AIM 1**). Further, while the fMRI methods developed and tested by us and others are now well established, the approach of using fMRI to localize targets for nerTMS intervention and as a way of predicting the possibility of post-stroke recovery ("point of no return"; **AIM 2**) is innovative; accomplishing this aim will establish fMRI as a clinical tool in rehabilitative medicine and allow its use for identifying intervention targets.

Figure 1 below illustrates the randomized, double-blind, sham controlled dosing trial of rTMS for the treatment of aphasia (**AIM 1**).

Figure 1. Diagram of the proposed nerTMS double-blind treatment protocol (**AIMS 1-2**) and associated testing ("AT qualitative and quantitative AT; AT – quantitative testing only).

[figure not shown]

Figure 2 below illustrates the open-label study of combined rTMS and CIAT for the treatment of aphasia (AIM 3).

[figure not shown]

Figure 2. Diagram of the proposed nerTMS+CIAT open-label treatment protocol (AIM 3) and associated testing (Abbreviations as in Figure 1)

DETAILED STUDY PROTOCOL

DAY 1 (enrollment)

Subject identified by study personnel (or referred to our team for possible study participation by clinicians in the area) will undergo screening for study participation:

The inclusion criteria are:

- Age \geq 19 years

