All these individuals already expressed their interest in participating in the Data Safety Monitoring Board for this study. Drs. [name] and [name] will be responsible for providing updated efficacy and tolerability data to the DSMB every six months (at least 2 weeks prior to the DSMB meeting). The DSMB will assess the risks and benefits of study participation to all subjects and based on this assessment the DSMB will provide a written report of their analyses and recommendation as to whether the study should continue, whether modification to the study are needed or if the study should be terminated. [name], in conjunction with the DSMB, will be responsible for making certain that the DSMB files their report to the IRBs and NINDS. The DSMB will also provide the investigator with a summary of their report that will include their recommendations.

Adverse events will be monitored during the study using clinical interviews and examinations that will be administered by a board certified neurologist ([name]) who has had more than 10 years experience conducting clinical investigations of stroke in adults. [name] (or in his absence another experienced neurologist) will be responsible for evaluating all adverse events during study visits, which will occur at the beginning and the completion of the study or more frequently as necessary. Further, the rTMS Team will supervise all nerTMS sessions and report any adverse events to the PI. Additionally, a study related physician (typically, [name]) is accessible by pager to patients, their legal guardians, hospital and research staff 24 hours/day, 7 days/week. Drs. [name] will be responsible for monitoring all baseline and post-baseline assessments.

An adverse event (AE) is any unexpected medical occurrence in a patient or clinical investigation subject who is administered a treatment (nerTMS and/or CIAT) and which does not necessarily have a causal relationship with the treatment. This includes any clinical change that occurs at any time following consent that does not typically occur in that subject and is considered clinically significant. The frequency and severity of all observed or volunteered AEs regardless of treatment group or suspected causal relationship to the study treatment will be recorded throughout the study. [name], with oversight from the DSMB, will be responsible for determining causal relationship between the study treatment and all AEs.

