Withdrawal from the study as a result of an AE or because of therapeutic measures taken to treat an AE will be at the discretion of [name]. If a subject withdraws or is withdrawn from the study for any reason, [name] will monitor subjects with any

ongoing AE until the AE is resolved or determined to be stable. All AEs (including those present during screening) will be reported. However, for analytics purposes, only post-baseline (randomization) AEs will be considered for calculating treatment group differences in AEs.

A serious adverse event (SAE) is any adverse experience occurring at during study participation that results in any of the following outcomes: death; a life threatening adverse drug experience; inpatient hospitalization or prolongation of existing hospitalization; a persistent or significant disability/incapacity. Important medical events that may not result in death, be life-threatening, or require hospitalization may be considered serious adverse experiences when, based on appropriate medical judgment of the study physician, they may jeopardize the patient and may require medical or surgical intervention to prevent one of the outcomes in this definition. The judgment of whether a particular AE meets the above criteria for an SAE for the proposed study will be determined by [name], in conjunction with the proposed DSMB. It will also be [name] responsibility to manage all SAEs and to make referrals for appropriate care, as necessary. All SAEs will be reported to the University of Alabama at Birmingham Institutional Review Board, the study DSMB, and the NINDS project officer within 72 hours of their discovery. The study blind may be broken at any point throughout the study as needed to protect the safety of a subject. All subject information will be de-identified when reporting SAEs. All AEs and SAEs will be entered into a database that is de-identified and password protected to ensure confidentiality. [name], in collaboration with [name], will ensure that all patients have appropriate follow-up care after their study participation.

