Depending on the issues and protocol, a DSMB meeting may have both Open and Closed meeting minutes. Meeting minutes should be distributed as soon as possible after the DSMB meeting. IRB needs to be included on the distribution list. At the time of IRB annual renewal, DSMB minutes will be required, if not already provided.

7. Statistical Monitoring Guidelines

Study will not be terminated if there is evidence that one of the treatment conditions has better side effects profile or efficacy unless statistically significant difference in favor of one of the treatment arms is observed in at least 50% of the variables.

8. Content of Reports for the DSMB

- Study number and title. Brief summary of the study design.
- Protocol amendments
- Status of accrual. If accrual is slower than expected, a plan for increasing enrollment.
- Status of participating sites (for Multi-Center trials)
- Compliance

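### The adverse event definition is limited to unexpected occurrences, so mild, expected stimulation effects need not be recorded and the between-arm tolerability comparison could be attenuated

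*Combined protocol and SAP*

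**What the plan says.** The Data Safety Monitoring Plan opens its safety definitions with "An adverse event (AE) is any unexpected medical occurrence in a patient or clinical investigation subject" who is given a treatment, named in parentheses as nerTMS and/or CIAT. The next sentence says that this includes any clinical change after consent that "does not typically occur in that subject and is considered clinically significant".

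Three later provisions rest on the same term:

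- **Recording rule:** "The frequency and severity of all observed or volunteered AEs regardless of treatment group or suspected causal relationship to the study treatment will be recorded".
- **Session reporting:** "the rTMS Team will supervise all nerTMS sessions and report any adverse events to the PI".
- **Analysis:** "only post-baseline (randomization) AEs will be considered for calculating treatment group differences in AEs".

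The evaluating neurologist sees adverse events at study visits, "which will occur at the beginning and the completion of the study or more frequently as necessary".

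Two other places give the comparison weight. The Innovation section says "we will determine the most efficacious and the safest dose of nerTMS". Section 7 of the DSMB charter (Statistical Monitoring Guidelines) sets out what happens if "one of the treatment conditions has better side effects profile or efficacy" is seen during the trial. That section is a stopping guideline; the planned comparison of adverse events between arms is the one in the Data Safety Monitoring Plan.

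**The concern.** Whether an event is expected is normally something recorded about it, not a test it must pass to be recorded. Here it is written into the definition. A mild effect that the treatment team anticipates from stimulation can therefore be left off the record by someone following the plan to the letter.

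What is at stake is the tolerability comparison between the nerTMS arms and sham, and the picture that the DSMB receives. If expected effects occur more often under active stimulation, leaving them out removes more events from the nerTMS arms than from the sham arm. The recorded difference then understates the true one. Events that were never written down cannot be recovered later by pooling arms or by descriptive reporting.

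**Working it through.** **Step 1: which events the text covers.** Setting the definitions in the Data Safety Monitoring Plan side by side gives four cases.

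| Type of event | Covered by | Recorded? |
|---|---|---|
| Serious, expected or not | SAE definition, which has no expectedness condition | Yes |
| Non-serious, unexpected | First sentence of the AE definition | Yes |
| Non-serious, expected, clinically significant and untypical for the subject | Second sentence | Yes |
| Non-serious, expected, not judged clinically significant | Neither sentence | Not required |

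**Step 2: whether a later provision closes the fourth case.**

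- The recording rule applies to events already classed as AEs. Its wording on causal relationship does not help, because causality and expectedness are different attributes.
- The rTMS team reports adverse events, which is the same defined term.
- Scheduled evaluation is at the start and completion of the study, or more often as needed. The Neurological Examination section puts the final examination about 3 months after the intervention, long after a transient session effect.
- No list of expected effects, solicited symptom checklist or separate tolerability form is described.

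Nothing in the text closes the gap.

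**Step 3: illustration of size.** The plan states no adverse event rate and no safety power, so there is no figure of its own to reproduce. Every rate below is an assumption. The group size is from Aim 1: 15 per group, with three groups receiving some nerTMS (3 × 15 = 45) and one receiving sham only.

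Let b be the background risk of a recorded AE (10% in both arms), e the risk of an expected mild effect (5% with sham; 20%, 40% or 60% with nerTMS), and c the share of expected effects that is recorded, equal in both arms.

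Recorded risk = 1 − (1 − b)(1 − e·c)

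Recorded difference = (1 − b) × c × (e with nerTMS − e with sham)

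For e = 40% and c = 1: nerTMS 1 − 0.9 × 0.6 = 46%; sham 1 − 0.9 × 0.95 = 14.5%; difference 31.5 points. For c = 0.5: nerTMS 1 − 0.9 × 0.8 = 28%; sham 1 − 0.9 × 0.975 = 12.25%; difference 15.75 points. Power is from an exact two-sided Fisher test at 0.05.

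| e with nerTMS | c | nerTMS | Sham | Difference (points) | Power, 15 v 15 | Power, 45 v 15 |
|---|---|---|---|---|---|---|
| 20% | 1 | 28% | 14.5% | 13.5 | 7% | 13% |
| 20% | 0.5 | 19% | 12.25% | 6.75 | 3% | 3% |
| 40% | 1 | 46% | 14.5% | 31.5 | 31% | 58% |
| 40% | 0.5 | 28% | 12.25% | 15.75 | 9% | 17% |
| 60% | 1 | 64% | 14.5% | 49.5 | 69% | 93% |
| 60% | 0.5 | 37% | 12.25% | 24.75 | 21% | 41% |
| any | 0 | 10% | 10% | 0 | – | – |

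The recorded difference is proportional to c. It reaches zero only if no expected effect is recorded at all.

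**The case against.** The strongest reply is that *unexpected* is loose wording for *untoward*. The surrounding text gives this some support. The same section counts events already present at screening as AEs, which fits badly with a strict test of unexpectedness. It records severity, which suggests that milder events are meant to be included. It provides for clinical interviews and supervised sessions. It also describes tolerability data as including AEs and SAEs, which leaves room for something wider. This reading is plausible, but no sentence says that expected effects are recorded, so the matter is left to individual judgement.

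A second reply is that the practical effect is small. The documents list no expected stimulation effects. They describe TBS as comfortable and well tolerated, report no adverse reactions in the pilot group, and call the stimulation subthreshold. Tolerability is not part of either hypothesis or any of the three aims; the safest-dose statement stands only in the Innovation section. With 15 per arm, power for AE differences is 7% to 31% in the two lower scenarios even with full recording. All of this stands, and it limits the weight of the point.

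A reader might also infer that clinical significance is a condition for recording every AE. The text does not support that: the phrase sits in a sentence that gives an inclusion under the definition, and an unexpected event need not meet it.

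**Conclusion.** The definition, followed literally, leaves non-serious, expected stimulation effects that are not judged clinically significant outside what must be recorded, and therefore outside the planned between-arm comparison. The comparison and the safest-dose statement could be attenuated toward no difference. This depends on two assumptions that the documents do not settle: that staff apply the wording literally, and that such effects are more frequent with nerTMS than with sham.

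A reader might go further and infer that the comparison is biased, or that nerTMS will look as tolerable as sham. The documents do not support either. They give no rates, and partial omission does not make the arms look equal. If 30% of nerTMS and 10% of sham subjects had such an effect (assumed) and half were left out, the record would show 15% against 5%, still a ratio of 3 to 1.

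Nor does the gap reach serious events or clinically significant changes untypical for the subject. The wording should be corrected because the change is cheap, not because harm has been shown.

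**What to change.** In the Data Safety Monitoring Plan:

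1. Define an AE as any untoward medical occurrence, whether or not expected, in any subject in any arm including sham. The present definition names only nerTMS and CIAT as treatments, although the recording rule suggests that sham subjects are meant to be covered.
2. State that the sentence that follows the definition is an example and not a condition for recording.
3. Record expectedness as an attribute of each AE, beside the severity already planned.

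The cost is one rewritten sentence, one clarification, one added item for each AE, and more mild events to record. The change does not alter any treatment or visit. It also leaves recording dependent on events being observed or volunteered, so it removes the definitional gap but does not guarantee complete recording.

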- LMCA stroke as indicated by the presence of aphasia and MRI lesion in the LMCA distribution
- Moderate aphasia (Token Test score between 40th and 90th percentile)
- Fluency in English
- Provision of written informed consent by the patient and/or the next of kin

The exclusion criteria include:

- Age less than 19 years
- Underlying degenerative or metabolic disorder or supervening medical illness
- Severe depression or other psychiatric disorder
- Positive pregnancy test in women of childbearing age
- Any contraindication to MRI/fMRI at 3T (i.e., intracranial metal implants, claustrophobia)
- Any contraindication to nerTMS (e.g., seizures or epilepsy)

Screening will also include a complete medical history, details of the precipitating event, physical examinations, complete baseline and ongoing vital sign assessments, neurological evaluations, laboratory results and diagnostic imaging performed. Screening assessments will be performed by the clinician involved in the care of the patient to determine subject eligibility criteria especially neurological examination, which will be documented as part of the patients' medical record.

For the randomized controlled trial (RTC; Figure 1), once informed consent and HIPAA authorization for research are obtained, the subject will be randomized. Randomization will be conducted by the study biostatistician and will be implemented using a standard sealed envelope process.

For the un-blinded observational study (OBS; Figure 2), once informed consent and HIPAA authorization for research are obtained, the subject will be scheduled for group therapy with CIAT where rTMS will be used as a primer for improved rehabilitation outcomes. Three to four subjects will be scheduled concurrently in order to achieve the required minimum of 3 subjects per CIAT therapy group. These subjects will not be randomized or blinded to the treatment.

A member of the research study staff will monitor the subjects for continued compliance with Inclusion and Exclusion Criteria. Those subjects who do not meet the continuation criteria will be terminated from the study.

DAY 2 (pre-nerTMS; days 1 and 2 may be combined)
All subjects (RTC or OBS) will undergo the same procedure

Data Collected for Study Enrollment (after signed consent):

Upon Admission:

Demographics

Medical history (including any chronic underlying disease and medications)

Contact information to include phone number

Time, date, and mechanism of stroke

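### No scheduled, standardised adverse-event questioning is set for the treatment weeks, so symptom-type AEs in people with aphasia may be under-recorded and could be captured differently by arm

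*Combined protocol and SAP*

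**What the plan says.** The capture rule is in the Data Safety Monitoring Plan: "The frequency and severity of all observed or volunteered AEs regardless of treatment group or suspected causal relationship to the study treatment will be recorded", and the sentence goes on to say that this applies throughout the study. Elicited events are not named.

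The same section does provide active follow-up: "Adverse events will be monitored during the study using clinical interviews and examinations that will be administered by a board certified neurologist". The neurologist evaluates AEs at study visits, "which will occur at the beginning and the completion of the study or more frequently as necessary". Two further routes are given. At treatment visits, "the rTMS Team will supervise all nerTMS sessions and report any adverse events to the PI". Outside them, a study physician "is accessible by pager to patients, their legal guardians, hospital and research staff 24 hours/day, 7 days/week".

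A comparison between arms is planned, for which "only post-baseline (randomization) AEs will be considered for calculating treatment group differences in AEs". Section 7 of the DSMB manual brings the side-effect profile into the stopping guideline, and the Innovation section promises to identify the safest dose of nerTMS.

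Neither the protocol nor the DSMB manual describes an AE question list, checklist, caregiver interview or aphasia-adapted form for the treatment weeks.

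The timing of the neurological examination is stated in two ways. Post-Intervention Procedures lists it among the procedures done within a week of the last intervention and again 3 months later. The Neurological Examination section gives enrollment and about 3 months after the intervention.

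**The concern.** Moderate aphasia is an entry requirement. Symptoms that staff cannot see, such as a headache that evening or an event at home, reach the record when someone reports them, and reporting takes language. Hypothesis 1 is that nerTMS improves language compared with sham. If it does so while AEs are still accruing, patients on active treatment may report more of the same symptoms; if it impairs language, they may report fewer.

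Two things are at stake. AEs of this kind may be under-counted in every arm. The difference between arms may also reflect how easily patients report as well as how well they tolerate treatment. With 15 patients per arm and safety forming part of the dose question, a few lost or added reports change the picture.

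**Working it through.** The documents give no AE rate, capture probability or test for AEs, so there is no planned figure to reproduce. The check has two parts.

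**1. Which routes operate in the treatment weeks.**

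- Fixed neurologist interviews: beginning and completion of the study. All 15 sessions (10 in the open-label group, OBS) lie between them.
- Extra neurologist visits as necessary: something must first be noticed or reported.
- rTMS team: present at every session and reports AEs, but no set question is specified.
- Pager: depends on a call from the patient, a guardian or staff.
- Neurological examination: on either statement of its timing, the first one after baseline follows the last session. The printed form lists signs and vital values and has no symptom or AE item.

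No route fixed for those weeks therefore puts the same question to every patient.

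**2. Scale, by assumption.** Let p be the true proportion of patients with a symptom, equal in both arms, and c the probability that it is recorded by any route.

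- Recorded proportion = p × c.
- Recorded risk ratio = c(active) / c(sham), because p cancels.
- Expected recorded patients = 15 × p × c, with 15 per arm from Aim 1.
- Chance that an arm records no case = (1 − p × c)^15.

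The values p = 20% to 60% and c = 50% to 90% are assumptions. Cells show recorded proportions, sham v active; expected patients of 15; and the exact probability that a two-sided Fisher test at 0.05 rejects. The test is chosen for illustration.

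| Capture, sham v active | Ratio | p = 20% | p = 40% | p = 60% |
|---|---|---|---|---|
| 60% v 60% | 1.00 | 12% v 12%; 1.8 v 1.8; 0.8% | 24% v 24%; 3.6 v 3.6; 1.8% | 36% v 36%; 5.4 v 5.4; 1.6% |
| 60% v 70% | 1.17 | 12% v 14%; 1.8 v 2.1; 1.1% | 24% v 28%; 3.6 v 4.2; 2.1% | 36% v 42%; 5.4 v 6.3; 2.2% |
| 60% v 80% | 1.33 | 12% v 16%; 1.8 v 2.4; 1.5% | 24% v 32%; 3.6 v 4.8; 3.0% | 36% v 48%; 5.4 v 7.2; 4.1% |
| 50% v 90% | 1.80 | 10% v 18%; 1.5 v 2.7; 2.8% | 20% v 36%; 3.0 v 5.4; 7.6% | 30% v 54%; 4.5 v 8.1; 14.0% |

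Equal capture leaves the ratio unbiased. Unequal capture distorts the descriptive ratio, but a falsely significant result exceeds 5% only in the widest gap, at p = 40% or 60%.

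Under-recording does not need unequal capture. At p = 20% and c = 60%, the chance that an arm records no case is (1 − 0.12)^15 = 0.147, against (1 − 0.20)^15 = 0.035 with full capture. At p = 40% it is (1 − 0.24)^15 = 0.016, against (1 − 0.40)^15 = 0.0005.

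**The case against.** The plan is not purely passive. It names neurologist interviews, allows more of them, supervises every session and lets guardians and staff call at any hour. Session count and supervision are the same in all randomised arms, and events that staff see do not depend on the patient's speech. Entry is limited to moderate aphasia and the consent process includes comprehension questions, so inability to report cannot be presumed. Sham comes first in the arms with one or two weeks of nerTMS, which limits how early language could diverge between arms. The only AE observation in the documents is that none occurred in the pilot patients.

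All of this stands. It makes differential capture less certain and confines the point to symptoms that staff cannot see. It does not supply a standard question during treatment.

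Four stronger readings may tempt a reader, and the documents do not support them:

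- *AEs in these weeks are recorded only if staff see them or the patient speaks up.* Guardians may report, and extra interviews are allowed.
- *Patients go unexamined for months.* One of the two statements on timing places an examination within a week of the last session.
- *Worsening of language would go unseen.* Five aphasia test sessions are scheduled. Discourse samples before, immediately after and 3 months after the intervention match sessions 1, 4 and 5, so sessions 2 and 3 appear to fall in between.
- *The rTMS team is unblinded because the personnel list does not mark it as blinded.* A missing label is weak evidence: Aim 1 describes a double-blind design, and the description of the rTMS procedure says that blinding is maintained in every arm.

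**Conclusion.** The concern holds in limited form. The plan fixes no scheduled, standardised, aphasia-accessible AE questioning for the treatment weeks, yet it plans to compare AEs between arms in people whose language the treatment is meant to change. Symptom-type AEs may be under-recorded and could be captured differently by arm.

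A between-arm bias is possible and not shown. It requires language to differ by arm while AEs are being reported, and its direction depends on the sign of the language effect. Its size cannot be derived from the documents; the ratios of 1.17 to 1.80 rest wholly on assumed capture probabilities. This is a cheap improvement worth making, not a defect that invalidates the design.

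**What to change.** Extend the capture rule to events that are observed, volunteered or elicited. In the randomised trial (RTC), have staff already present ask one short, fixed set of yes/no AE questions, with picture or pointing support and caregiver input where available. Ask it identically in all four arms, once at each existing session visit to cover events since the last visit, and again at the post-treatment and 3-month visits. Record the source of each AE. Base the arm comparison on the elicited items and report observed and volunteered AEs beside them. The OBS group can use the same form for safety only, since it has no randomised comparison.

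The cost is a form with adapted materials and a few minutes per visit. That is 60 × (15 + 2) = 1,020 short queries in the randomised trial and 20 × (10 + 2) = 240 in OBS, with no added visits. Recorded AE counts will rise in every arm, including sham. Answers will still depend on comprehension, so the query reduces the problem without removing it.

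Separately, reconcile the two statements of neurological examination timing in Post-Intervention Procedures and Neurological Examination.

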All procedures will be performed within 1 week of the last rTMS/CIAT intervention and then 3 months later following the above described protocols.

Upon completion of the above procedures subjects will be dismissed from the study. Further follow up will be provided by primary neurologist or primary care provider.

NEUROLOGICAL EXAMINATION

Standard neurological examination will be performed by [name] or his designee at the initiation of the study (after the patient signs the consent form) and after completion of the study (around the time of final neuropsychological testing of aphasia ~3 months after completion of the intervention). This examination will include:

	Study enrollment	Study termination	Change*
Date of exam			
Vital Signs			
Blood Pressure			
Heart Rate			
Finger stick blood glucose			
Cranial nerve examination			
Visual fields			
Ophtalmoscopic examination			
Pupils			
Eye movements (CN 3,4,6)			
Facial symmetry			
Auditory assessment			
Palate			
Shrug			
Tongue examination (midline)			
Muscle strength right upper extremity (MRC)			
Muscle strength left upper extremity (MRC)			
Muscle strength right lower extremity (MRC)			
Muscle strength left lower extremity (MRC)			
Muscle stretch reflexes right upper extremity			
Muscle stretch reflexes left upper extremity			
Muscle stretch reflexes right lower extremity			
Muscle stretch reflexes left lower extremity			
Coordination right upper extremity			
Coordination left upper extremity			
Gait			
Mechanism of ischemic stroke**			

* (-1 = worse after intervention; 1 = improved after intervention; 0 = no change)

** (small vessel = 1; large vessel = 2; embolic = 3 ; hypercoagulable state = 4; unknown = 5)

Participants requiring additional protections

Regarding cognitively impaired subjects: All subjects will be enrolled in the study based on voluntary basis. The patients will not be approached until the purposed of the study is explained to the patient by the physician directly involved in the care of the patient and a verbal permission is obtained from the patient (and family member/significant other if appropriate) regarding the contact with the study personnel. After screen is complete and the subject is found to be eligible, she/he will receive the consent form for review. After at least 24 hours the patient will be contacted regarding the study. If interested and have correctly answered all questions on both the Consent Form

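### No provision for collecting later safety and language outcomes from participants who are withdrawn or terminated from the study

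*Combined protocol and SAP*

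**What the plan says.** **Exit for an AE (Data Safety Monitoring Plan).** "Withdrawal from the study as a result of an AE or because of therapeutic measures taken to treat an AE will be at the discretion"; a named role decides. The paragraph speaks of leaving the study; it does not mention stopping sessions while staying in follow-up.

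**After exit (same paragraph).** "If a subject withdraws or is withdrawn from the study for any reason", that role monitors subjects who have an "ongoing AE until the AE is resolved or determined to be stable". No other activity after exit is described, apart from a general assurance at the end of that part of the plan that patients will have appropriate clinical follow-up care.

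**Exit for failing criteria (DAY 1, enrollment).** Staff check continued compliance with the inclusion and exclusion criteria during the study. "Those subjects who do not meet the continuation criteria will be terminated from the study". The exclusion criteria include "Any contraindication to nerTMS (e.g., seizures or epilepsy" and supervening medical illness.

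**Scheduled assessments (Post-Intervention Procedures).** Aphasia testing, fMRI and the neurological exam are listed, with this timing: "All procedures will be performed within 1 week of the last rTMS/CIAT intervention and then 3 months later following the above described protocols". Subjects are dismissed once these are complete. The Neurological Examination section, however, places that exam only at study initiation and about 3 months after the intervention.

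**AE windows (Data Safety Monitoring Plan).** AEs are recorded for the duration of the study, a serious AE is defined by its occurrence while the subject is participating, and AEs after randomisation enter the comparison between treatment groups.

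**The concern.** Stopping stimulation is a treatment decision. Leaving the study is a data decision. The protocol treats the second as the consequence of both exit rules and never describes the first on its own. A participant withdrawn for an AE, or terminated because a criterion is no longer met, then has no stated route to the assessments that everyone else receives.

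This matters because both exits can be related to how treatment was tolerated. Aim 1 compares four stimulation schedules for efficacy and dose, and the Innovation section promises to identify the safest dose. If exits differ between arms, the comparison of later AEs rests on unequal observation, and the language comparison rests on those who remained rather than on those randomised. The documents state no analysis set and no missing-data rule that would limit the effect.

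**Working it through.** The plan states no figure on this point, and no AE rate, dropout rate, effect size, SD, alpha or power. The main check is therefore a comparison of the text; the arithmetic gives scale only.

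**1. What each status provides**

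- *Stays in the study and completes the sessions:* post-treatment and 3-month aphasia testing and fMRI, neurological examination, and AE recording until dismissal after the 3-month procedures.
- *Stops sessions but stays in the study:* not described. Post-Intervention Procedures counts time from the last intervention, not from a completed course, so it can be read to cover this person.
- *Withdrawn for an AE, or terminated for a failed criterion:* monitoring of an AE still ongoing at exit, until resolved or stable. No outcome assessment and no collection of AEs with later onset is described.

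**2. Length of observation.** In the randomised part: 3 weeks of sessions, up to 1 week to the post-treatment visit, and about 13 weeks (3 months) to the last visit, so 3 + 1 + 13 = about 17 weeks. Someone withdrawn at the end of week 1 with no ongoing AE has 1 week of described observation.

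**3. Share of an arm.** Aim 1 sets 15 per group. Losing k participants removes k/15: 1/15 = 6.7%, 2/15 = 13.3%, 3/15 = 20.0%.

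**4. Possible shift in one arm's mean (illustration).** Let the completers' mean be m and the mean of the k lost be m − D, in SD units.

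- All-randomised mean = m − (k/15)·D, so the completers' mean is off by (k/15)·D.
- With D assumed between 0.5 and 1.0: k = 1 gives 0.03 to 0.07 SD; k = 2 gives 0.07 to 0.13 SD; k = 3 gives 0.10 to 0.20 SD.
- The shift in a contrast between arms is the difference of two such terms. It is zero if both arms lose the same number with the same D, and its sign depends on D and on which arm loses more.

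**5. Loss of precision (illustration: two-sided 5%, two arms, normal approximation).**

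- Detectable difference at 80% power = (1.960 + 0.842)·√(1/15 + 1/n). At n = 15 this is 1.023 SD; at n = 12, 1.085 SD.
- Power for a 1.0 SD difference falls from 78.2% to 73.3%.
- For an event that appears only after exit, zero events observed gives an exact one-sided 95% upper limit of 1 − 0.05^(1/n): 18.1% at n = 15 and 22.1% at n = 12.

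The precision cost of a few losses is small. The issue is selective loss.

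**6. Two sets of statements to reconcile**

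- A seizure during the study is an AE, where withdrawal is discretionary. It also appears as an example under the exclusion criteria, against which staff monitor continued compliance and whose failure appears to mean termination. The term continuation criteria is not defined, so it is unclear which rule applies.
- Post-Intervention Procedures puts the neurological exam within 1 week and again at 3 months; the Neurological Examination section has only the 3-month exam after treatment.

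**The case against.** Several stronger readings are tempting, and the documents do not support them.

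- *That an AE leads to withdrawal.* It does not do so automatically. The AE paragraph makes withdrawal discretionary, so a participant with an AE may stay and be assessed on schedule. This stands, and the point is limited to people who are actually withdrawn or terminated.
- *That assessments are cancelled for anyone who stops sessions.* No text cancels them, and the timing from the last intervention may cover someone who stops early but remains in the study. This also stands.
- *That the harm itself goes unrecorded.* The AE that prompts withdrawal is recorded and counted in the group comparison. Only later-onset AEs and later assessments are at risk.
- *That the bias favours nerTMS.* This would need exits to concentrate in arms with more active stimulation and those leaving to do worse. The documents give no such data, and the safety section reports no adverse reactions in the pilot group. Similarly, a reader could assume that those lost gain nothing and derive an overstatement of 15/14 − 1 = 7% to 15/12 − 1 = 25% for 1 to 3 losses. That describes one arm's mean under an assumed zero gain, not the contrast with sham.
- *That the two exit rules flatly contradict each other on a seizure.* The AE rule may be meant as the specific rule, and the continuation criteria are undefined. It is an ambiguity to reconcile.

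Two possible answers do not close the gap. Appropriate follow-up care is clinical care, not research data. The AE definition reaches any time after consent, but no contact or visit is provided through which a withdrawn person's later AEs would be found.

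**Conclusion.** The concern holds in a limited form. The protocol does not separate stopping stimulation from leaving the study. Under both exit rules, a participant who leaves is followed only for an ongoing AE; nothing provides for later AEs or for the post-treatment and 3-month assessments. Because exits can be linked to tolerability, this could bias the between-arm AE and efficacy comparisons.

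Each loss is 6.7% of an arm. With 1 to 3 losses, and an assumed difference of 0.5 to 1.0 SD between those lost and those retained, one arm's completer mean shifts by 0.03 to 0.20 SD. The direction and actual size cannot be known from the documents, since the number of exits, their distribution over arms and the outcomes of those who leave are all unstated. The change should be made because it is cheap and the missing data could not be recovered later.

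**What to change.** Leave the decision on stopping treatment, and who takes it, as it is. Change only data collection:

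1. In the Data Safety Monitoring Plan and in DAY 1 (enrollment), add that participants who stop sessions, or who are withdrawn for an AE or a failed continuation criterion, are still invited, unless they withdraw consent, to the post-treatment and 3-month assessments (fMRI only where not contraindicated) and to AE collection through the 3-month visit.
2. State that randomised participants are analysed in the arm to which they were randomised.
3. Reconcile the AE withdrawal rule with the continuation-criteria rule for an on-study event, such as a seizure, that falls under both. This review takes no position on which rule is right.
4. Reconcile Post-Intervention Procedures with the Neurological Examination section on the timing of the post-treatment examination, again without a view here on which is right.

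The cost is protocol wording and staff effort to bring back people who have stopped treatment. The assessments are already on the study schedule, so no new visit type is needed.
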